**Table 14.3.2. Summary of Physical examination**

	CLL/SLL (N=xx)	MCL (N=xx)	Total (N=xx)
	n (%)	n (%)	n (%)
Visit x			
Physical examination performed			
Yes	xx (xx.xx)	xx (xx.xx)	xx (xx.xx)
No	xx (xx.xx)	xx (xx.xx)	xx (xx.xx)
System x			
Normal	xx (xx.xx)	xx (xx.xx)	xx (xx.xx)
Abnormal NCS	xx (xx.xx)	xx (xx.xx)	xx (xx.xx)
Abnormal CS	xx (xx.xx)	xx (xx.xx)	xx (xx.xx)

- The Capital "N" in the column header represents the total number Full Analysis Set.
- The small "n" in summary statistics represents the total number of Patients.
- Percentages in the "Physical Examination performed" rows are based on number of patient in each group.
- Percentages in the "System x" rows are based on number of Patient Physical Examination performed in each group.
- Programmer Note: Generate summaries for the following System x :General Appearance, Skin, Eyes, Ears, Nose, Throat, Lungs, Heart, Abdomen, Extermities, Musculoskeletal System, Lymphatic System, Nervous System, Liver, Spleen and Other.
- NCS= Non-clinically significant
- CS= clinically significant
- Programme Note: Visit x- Visit 1 up to Visit 8
- Source :Listing 16.2.13

Document Title:	Document ID:	BP04-01
Statistical Analysis Plan	Version Number:	3.1
	Effective Date:	25-Nov-2021

**Table 14.3.3. Summary of Electrocardiogram**

	CLL/SLL (N=xx)	MCL (N=xx)	Total (N=xx)
Visit x			
ECG Performed			
Yes	xx (xx.xx)	xx (xx.xx)	xx (xx.xx)
No	xx (xx.xx)	xx (xx.xx)	xx (xx.xx)
Heart rate (bpm)			
n	xx	xx	xx
Missing	xx	xx	xx
Mean (SD)	xx.x (xx.xx)	xx.x (xx.xx)	xx.x (xx.xx)
Median	xx.x	xx.x	xx.x
(min, max)	(xx.xx, xx.xx)	(xx.xx, xx.xx)	(xx.xx, xx.xx)
QRS (ms)			
n	xx	xx	xx
Missing	xx	xx	xx
Mean (SD)	xx.x (xx.xx)	xx.x (xx.xx)	xx.x (xx.xx)
Median	xx.x	xx.x	xx.x
(min, max)	(xx.xx, xx.xx)	(xx.xx, xx.xx)	(xx.xx, xx.xx)
PR (ms)			
n	xx	xx	xx
Missing	xx	xx	xx
Mean (SD)	xx.x (xx.xx)	xx.x (xx.xx)	xx.x (xx.xx)
Median	xx.x	xx.x	xx.x
(min, max)	(xx.xx, xx.xx)	(xx.xx, xx.xx)	(xx.xx, xx.xx)
RR (ms)			
n	xx	xx	xx
Missing	xx	xx	xx
Mean (SD)	xx.x (xx.xx)	xx.x (xx.xx)	xx.x (xx.xx)
Median	xx.x	xx.x	xx.x
(min, max)	(xx.xx, xx.xx)	(xx.xx, xx.xx)	(xx.xx, xx.xx)
QT (ms)			
n	xx	xx	xx
Missing	xx	xx	xx
Mean (SD)	xx.x (xx.xx)	xx.x (xx.xx)	xx.x (xx.xx)
Median	xx.x	xx.x	xx.x
(min, max)	(xx.xx, xx.xx)	(xx.xx, xx.xx)	(xx.xx, xx.xx)
QTcB (ms)			
n	xx	xx	xx
Missing	xx	xx	xx
Mean (SD)	xx.x (xx.xx)	xx.x (xx.xx)	xx.x (xx.xx)
Median	xx.x	xx.x	xx.x
(min, max)	(xx.xx, xx.xx)	(xx.xx, xx.xx)	(xx.xx, xx.xx)

- The Capital "N" in the column header represents the total number Full Analysis Set.
- The small "n" in summary statistics represents the total number of Patients.
- SD = Standard Deviation, min=minimum, max=maximum
- Visit x: Visit 1 up to Visit 8
- Source :Listing 16.2.14

Document Title:	Document ID:	BP04-01
Statistical Analysis Plan	Version Number:	3.1
	Effective Date:	25-Nov-2021

**Table 14.3.4.1. Summary of Laboratory assessment for Haematology**

	CLL/SLL (N=xx)	MCL (N=xx)	Total (N=xx)
Visit x			
Sample Collected			
Yes	xx (xx.xx)	xx (xx.xx)	xx (xx.xx)
No	xx (xx.xx)	xx (xx.xx)	xx (xx.xx)
Haematology Parameter x			
n	Xx	Xx	Xx
Missing	Xx	Xx	Xx
Mean (SD)	xx.x (xx.xx)	xx.x (xx.xx)	xx.x (xx.xx)
Median	xx.x	xx.x	xx.x
(min, max)	(xx.xx, xx.xx)	(xx.xx, xx.xx)	(xx.xx, xx.xx)

- The Capital "N" in the column header represents the total number Full Analysis Set.
- The small "n" in summary statistics represents the total number of Patients.
- SD = Standard Deviation, min=minimum, max=maximum
- Percentages in the "Sample collected" rows are based on number of patient in each group.
- Programmer Note: Generate summaries for the following Haematology parameters x: Haematocrit (%), Haemoglobin (g/dL), Neutrophils (%), Basophils (%), Eosinophils (%), Monocytes(%), Absolute Lymphocytes Count(thou/μL), Percentage Lymphocytes (%), Reticulocyte (%), Absolute Neutrophils Count (thou/μL), Platelet Count (thou/μL), Total leukocyte count(thou/μL).
- Programmer Note Visit x: Visit 1 up to Visit 8
- Source :Listing 16.2.15.1

Document Title:	Document ID:	BP04-01
Statistical Analysis Plan	Version Number:	3.1
	Effective Date:	25-Nov-2021

**Table 14.3.4.2. Summary of Laboratory assessment for Biochemistry**

	CLL/SLL (N=xx)	MCL (N=xx)	Total (N=xx)
Visit x			
Sample Collected			
Yes	xx (xx.xx)	xx (xx.xx)	xx (xx.xx)
No	xx (xx.xx)	xx (xx.xx)	xx (xx.xx)
Biochemistry Parameter x			
n	xx	xx	xx
Missing	xx	xx	xx
Mean (SD)	xx.x (xx.xx)	xx.x (xx.xx)	xx.x (xx.xx)
Median	xx.x	xx.x	xx.x
(min, max)	(xx.xx, xx.xx)	(xx.xx, xx.xx)	(xx.xx, xx.xx)

- The Capital "N" in the column header represents the total number Full Analysis Set.
- The small "n" in summary statistics represents the total number of Patients.
- SD = Standard Deviation, min=minimum, max=maximum
- Percentages in the "Sample collected" rows are based on number of patient in each group.
- Programmer Note: Generate summaries for the following parameters x – Albumin (g/dL), Glucose (mg/dL), Amylase (U/L), Lipase (U/L), Alkaline phosphatase (U/L), Lactate dehydrogenase (U/L), Alanine aminotransferase (U/L), Aspartate aminotransferase (U/L), Potassium (mmol/L), Bicarbonate (mmol/L), Sodium (mmol/L), Calcium (mg/dL), Total bilirubin (mg/dL), Chloride(mmol/L), Total Protein (g/dL), Creatinine (mL/min/1.73m^2), Urea (mg/dL), Blood Urea Nitrogen (mg/dL), Gamma-glutamyltransferase (U/L), Magnesium (mg/dL), Haptoglobin (g/L) and b2-microglobulin(ng/ML).
- Programmer Note Visit x: Visit 1 up to Visit 8.
- Source :Listing 16.2.15.2

Document Title:	Document ID:	BP04-01
Statistical Analysis Plan	Version Number:	3.1
	Effective Date:	25-Nov-2021

**Table 14.3.4.3. Summary of Laboratory assessment for Serology**

	CLL/SLL (N=xx)	MCL (N=xx)	Total (N=xx)
	n (%)	n (%)	n (%)
Sample Collected			
Yes	xx (xx.xx)	xx (xx.xx)	xx (xx.xx)
No	xx (xx.xx)	xx (xx.xx)	xx (xx.xx)
HIV			
Positive	xx (xx.xx)	xx (xx.xx)	xx (xx.xx)
Negative	xx (xx.xx)	xx (xx.xx)	xx (xx.xx)
Active Cytomegalovirus (CMV) infection			
Positive	xx (xx.xx)	xx (xx.xx)	xx (xx.xx)
Negative	xx (xx.xx)	xx (xx.xx)	xx (xx.xx)
Hepatitis B surface antigen (HBsAg)			
Positive	xx (xx.xx)	xx (xx.xx)	xx (xx.xx)
Negative	xx (xx.xx)	xx (xx.xx)	xx (xx.xx)
Hepatitis B surface antibody (HBsAb)			
Positive	xx (xx.xx)	xx (xx.xx)	xx (xx.xx)
Negative	xx (xx.xx)	xx (xx.xx)	xx (xx.xx)
Anti-HBc antibody			
Positive	xx (xx.xx)	xx (xx.xx)	xx (xx.xx)
Negative	xx (xx.xx)	xx (xx.xx)	xx (xx.xx)
Anti-HCV antibody			
Positive	xx (xx.xx)	xx (xx.xx)	xx (xx.xx)
Negative	xx (xx.xx)	xx (xx.xx)	xx (xx.xx)

- The Capital "N" in the column header represents the total number Full Analysis Set.
- The small "n" in summary statistics represents the total number of Patients.
- Percentage rows are based on number of patient in each group  
Percentage in the "HIV", "Active Cytomegalovirus (CMV) infection", "Hepatitis B surface antigen (HBsAg)", "Hepatitis B surface antibody (HBsAb)", "Anti-HBc antibody" and "Anti-HCV antibody" rows are based on /nuber of Patient Sample Collected.
- Source :Listing 16.2.15.4

Document Title:	Document ID:	BP04-01
Statistical Analysis Plan	Version Number:	3.1
	Effective Date:	25-Nov-2021

Table 14.3.5. Summary of Vital Signs

	CLL/SLL (N=xx)	MCL (N=xx)	Total (N=xx)
Visit x			
Vital Signs Collected			
Yes	xx (xx.xx)	xx (xx.xx)	xx (xx.xx)
No	xx (xx.xx)	xx (xx.xx)	xx (xx.xx)
Weight (Kg)			
n	Xx	Xx	Xx
Missing	Xx	Xx	Xx
Mean (SD)	xx.x (xx.xx)	xx.x (xx.xx)	xx.x (xx.xx)
Median	xx.x	xx.x	xx.x
(min, max)	(xx.xx, xx.xx)	(xx.xx, xx.xx)	(xx.xx, xx.xx)
Heart rate (bpm)			
n	Xx	Xx	Xx
Missing	Xx	Xx	Xx
Mean (SD)	xx.x (xx.xx)	xx.x (xx.xx)	xx.x (xx.xx)
Median	xx.x	xx.x	xx.x
(min, max)	(xx.xx, xx.xx)	(xx.xx, xx.xx)	(xx.xx, xx.xx)
Respiratory rate (Breaths/min)			
n	Xx	Xx	Xx
Missing	Xx	Xx	Xx
Mean (SD)	xx.x (xx.xx)	xx.x (xx.xx)	xx.x (xx.xx)
Median	xx.x	xx.x	xx.x
(min, max)	(xx.xx, xx.xx)	(xx.xx, xx.xx)	(xx.xx, xx.xx)
Systolic Blood Pressure (mmHg)			
n	Xx	Xx	Xx
Missing	Xx	Xx	Xx
Mean (SD)	xx.x (xx.xx)	xx.x (xx.xx)	xx.x (xx.xx)
Median	xx.x	xx.x	xx.x
(min, max)	(xx.xx, xx.xx)	(xx.xx, xx.xx)	(xx.xx, xx.xx)
Diastolic Blood Pressure (mmHg)			
n	xx	xx	xx
Missing	xx	xx	xx
Mean (SD)	xx.x (xx.xx)	xx.x (xx.xx)	xx.x (xx.xx)
Median	xx.x	xx.x	xx.x
(min, max)	(xx.xx, xx.xx)	(xx.xx, xx.xx)	(xx.xx, xx.xx)
Temperature (F)			
n	xx	xx	xx
Missing	xx	xx	xx
Mean (SD)	xx.x (xx.xx)	xx.x (xx.xx)	xx.x (xx.xx)
Median	xx.x	xx.x	xx.x
(min, max)	(xx.xx, xx.xx)	(xx.xx, xx.xx)	(xx.xx, xx.xx)

- The Capital "N" in the column header represents the total number Full Analysis Set.
- The small "n" in summary statistics represents the total number of Patients.
- SD = Standard Deviation, min=minimum, max=maximum ;Percentage rows are based on the number of Full Analysis Set.
- Visit x: Visit 1 up to Visit 8 ; Source :Listing 16.2.16

Document Title:	Document ID:	BP04-01
Statistical Analysis Plan	Version Number:	3.1
	Effective Date:	25-Nov-2021

**Table 14.3.6. Summary of ECOG**

ECOG performed	CLL/SLL	MCL	Total
	(N=xx)	(N=xx)	(N=xx)
	n (%)	n (%)	n (%)
Visit x			
ECOG Grade			
0	xx (xx.xx)	xx (xx.xx)	xx (xx.xx)
1	xx (xx.xx)	xx (xx.xx)	xx (xx.xx)
2	xx (xx.xx)	xx (xx.xx)	xx (xx.xx)
3	xx (xx.xx)	xx (xx.xx)	xx (xx.xx)
4	xx (xx.xx)	xx (xx.xx)	xx (xx.xx)
5	xx (xx.xx)	xx (xx.xx)	xx (xx.xx)

- The Capital "N" in the column header represents the total number Full Analysis Set.
- The small "n" in summary statistics represents the total number of Patients.
- Percentage rows are based on number of patient in each group.
- Programme Note: Visit x- Visit 1 up to Visit 8.
- Source :Listing 16.2.17

Document Title:	Document ID:	BP04-01
Statistical Analysis Plan	Version Number:	3.1
	Effective Date:	25-Nov-2021

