8.1 Efficacy and Safety assessments

8.1.1 Efficacy Assessment

Objective Response

All patients who receive Acalabrutinib capsule 100 mg BID will be evaluated for efficacy once every 03 months during the treatment phase. The following assessments must be performed every three treatment cycles: tumour assessment, ECOG performance status, and partial remission (PR), partial response with lymphocytosis (PR-L) and complete remission (CR).

A characteristic feature of BTK inhibitor is that it may transiently increase the peripheral lymphocyte count while the lymph nodes are shrinking and patients are improving. Some patients were taken off study very early in ibrutinib trials because their lymphocyte count began to go up and it was assumed that they were progressing. The transient lymphocytosis is now understood to be an effect of redistributing parts of the disease into the blood. It is not considered as a sign of disease progression. There is now a response criterion known as PRL, which refers to patients who have a greater than 50% shrinkage of nodal disease and who fulfil all criteria of partial response (PR) except for a persistent lymphocytosis. (Woyach et al., 2014) In the present study the objective response will evaluate PR, PR-L, and CR.

The efficacy endpoint will be objective response, defined as the proportion of patients achieving either a PR or CR per the iwCLL 2018 criteria for CLL/SLL (Hallek et al., 2018) and Lugano classification for NHL for MCL (Cheson et al., 2014) as presented in Table 4 and Table 5, respectively. Efficacy will be based on objective response [Complete Remission (CR) + Partial Remission (PR)] via Computed Tomography (CT) scans or Magnetic Resonance Imaging (MRI).

Table 4: Response (CR and PR) definition after treatment of CLL/SLL patients (Hallek et al., 2018)

Parameter	Complete Remission (CR)	Partial Remission (PR)
Lymph nodes	None ≥ 1.5 cm	Decrease $\geq 50\%$ from baseline*
Liver and/or spleen size†	Spleen size < 13 cm; liver size normal	Decrease $\geq 50\%$ from baseline
Constitutional symptoms	None	any
Circulating lymphocyte count	Normal	Decrease $\geq 50\%$ from baseline
Platelet count	$\geq 100 \times 10^9/L$	$\geq 100 \times 10^9/L$ or increase $\geq 50\%$ over baseline
Haemoglobin	≥ 11.0 g/dL (untransfused and without erythropoietin)	≥ 11.0 g/dL or increase $\geq 50\%$ over baseline

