## 3. Population Analysis Set

### 3.1 Full Analysis Set

The Full Analysis Set (FAS) will consist of all enrolled Patients who received at least one dose of Acabrutinib.

Document Title:	Document ID:	BP04-01
Statistical Analysis Plan	Version Number:	3.1
	Effective Date:	25-Nov-2021

The FAS will be used for all analyses of safety and efficacy.

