#### 6.3.1 Primary Endpoint Analysis

Primary Endpoint evaluations will include adverse event monitoring, physical examinations, ECG monitoring, clinical laboratory investigations (haematology and biochemistry), vital sign measurements, ECOG performance status and death as observed by the Investigator.

Adverse Events (AEs), Serious Adverse Events (SAEs), and AEs of Special Interest (AESI) will be summarized using frequencies and percentages.

Physical examination will be collected as per visit scheduled. Physical examination results (normal /abnormal) from scheduled visits will be summarized for each body system. A listing will be provided for the Normal/abnormal physical examination parameters.

A 12-lead electrocardiogram (ECG) will be performed as per visit scheduled. ECG results (normal, abnormal clinically insignificant, abnormal clinically significant) will be summarized as counts and percentage.

Laboratory investigations (haematology and biochemistry) data will be collected as per visit scheduled. Laboratory values will be presented using the International System of Units (SI units). Observed values will be summarized descriptively (n, mean, median, standard deviation, minimum, and maximum values). A listing will be provided which contains data for each laboratory parameter.

Document Title:	Document ID:	BP04-01
Statistical Analysis Plan	Version Number:	3.1
	Effective Date:	25-Nov-2021

Vital signs will be performed as per visit scheduled. Vital signs parameters include Systolic Blood Pressure, Diastolic Blood Pressure, Heart Rate, Respiratory rate and Temperature. Descriptive summaries (n, mean, median, standard deviation, minimum and maximum values) of observed values in each vital sign parameter at each assessment visit will be presented. A listing will be provided for all vital signs parameters assessments.

ECOG will be performed as per visit scheduled. ECOG performance status will be summarized as counts and percentage.

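### By-visit ECOG percentages in SAP Table 14.3.6 use the whole FAS as denominator with no assessed or missing row, so they are diluted wherever assessments are absent and cannot be compared cleanly between visits

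*SAP*

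**What the plan says.** SAP section 6.3.1 lists ECOG among the primary endpoint evaluations. On its analysis it says only "ECOG will be performed as per visit scheduled" and "ECOG performance status will be summarized as counts and percentage". The rest is left to the shell of Table 14.3.6:

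- **Visits:** "Programme Note: Visit x- Visit 1 up to Visit 8".
- **Column N:** the capital N "in the column header represents the total number Full Analysis Set". SAP section 3.1 defines that set: "The Full Analysis Set (FAS) will consist of all enrolled Patients who received at least one dose of" acalabrutinib. A patient who leaves later therefore stays in N at every visit.
- **Percentages:** "Percentage rows are based on number of patient in each group".
- **Rows:** grades 0 to 5 only. The corner label refers to ECOG being performed, but there is no Yes/No row, no number assessed and no missing count. Listing 16.2.17 has no performed column either.

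Other safety shells deal with absent assessments. In Table 14.3.2 (physical examination) the result "rows are based on number of Patient Physical Examination performed in each group". The ECG, haematology, biochemistry and vital-sign tables show n and Missing. Serology and urine pregnancy results are divided by the patients tested.

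On timing, protocol section 8.1.1 states: "The following assessments must be performed every three treatment cycles: tumour assessment, ECOG performance status". Protocol Table 1, repeated in SAP section 2.2.5, marks ECOG at screening, in the column for Cycles 1 to 6 (Visits 2 to 7) and at end of treatment (Visit 8).

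**The concern.** A by-visit table of a status scale is read across visits to see whether patients are getting better or worse. With a fixed denominator and no missing row, each printed percentage mixes the grade distribution among those seen with the fraction seen. A change between visits may reflect either one, and the table does not separate them.

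The SAP gives no missing-data rule for ECOG and no change from baseline, so nothing elsewhere in the plan corrects this. The differing schedules add to the problem: if an assessment was not done because a site read section 8.1.1 as setting the frequency, that absence would also lower the percentages without being shown.

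**Working it through.** The plan states no ECOG figure and no expected dropout or missing rate, so there is nothing to reproduce. The check compares the planned percentage with one based on patients assessed.

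**Inputs.** From the documents: N = 90 (CLL/SLL) and N = 10 (MCL), the planned cohort sizes. Assumed: baseline ECOG 0/1/2 = 36/45/9 of 90 (40/50/10%), no patient changes grade, and 5% to 30% are unassessed at a visit.

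**Formulas.** Let c be the number at a grade and a the number assessed at the visit.

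- Planned: c / N
- Assessed-only: c / a
- Hence planned = assessed-only × (a / N), and the grade rows sum to a / N.

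**Missing evenly across grades, 20% unassessed.** a = 0.80 × 90 = 72. Expected counts are 28.8, 36 and 7.2.

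- Planned: 28.8/90 = 32.0%, 36/90 = 40.0%, 7.2/90 = 8.0% (sum 80%)
- Assessed-only: 28.8/72 = 40.0%, 36/72 = 50.0%, 7.2/72 = 10.0%, unchanged from baseline

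| Unassessed | Planned ECOG 0-1 (true 90%) | Planned ECOG 2 (true 10%) |
|---|---|---|
| 5% | 85.5% | 9.5% |
| 10% | 81.0% | 9.0% |
| 20% | 72.0% | 8.0% |
| 30% | 63.0% | 7.0% |

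The good-status share and the poor-status share both fall.

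**Missing selectively, 9 of 90 (10%) unassessed, so a = 81.**

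- Only ECOG 2 patients leave: planned 40.0/50.0/0.0%; assessed-only 36/81 = 44.4%, 45/81 = 55.6%, 0%.
- Only ECOG 0 patients leave: planned 27/90 = 30.0%, then 50.0% and 10.0%; assessed-only 27/81 = 33.3%, 45/81 = 55.6%, 9/81 = 11.1%.

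The planned table looks like improvement in the first case (ECOG 2 disappears) and like deterioration in the second (ECOG 0-1 falls from 90% to 80%). In the first case the assessed-only version shows 100% at ECOG 0-1, so changing the denominator does not remove selective dropout.

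**Small cohort.** One missing patient removes 1/10 = 10 points from the MCL column and 1/90 = 1.11 points from the CLL/SLL column.

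**Which visits.** Protocol sections 4.1.2 and 4.1.3 have patients who stop before Day 168 assessed as at end of treatment, and Table 1 marks ECOG there. If those assessments are stored as Visit 8, the dilution falls on the visits between stopping and Visit 8. If they stay at the visit where they occurred, it reaches Visit 8 too. The SAP does not say which.

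**Schedules.** Table 1 gives eight ECOG time points. Read as the only schedule, and placed at the response visits of SAP Table 14.2.1 (Visits 5 and 8) plus baseline, section 8.1.1 would leave Visits 2, 3, 4, 6 and 7 with no required ECOG: 5 of 8.

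**The case against.** The strongest reply is that little is hidden. The table prints counts, so the number assessed is the sum of the grade rows. Listing 16.2.17 shows every ECOG result, and Table 14.1.1 gives discontinuations with reasons. No hypothesis is tested, and SAP section 6.1.1 names adverse events, not ECOG, as the primary endpoint. Tables 14.1.4 and 14.2.1 also use group N without a missing row, and the n and Missing rows in the laboratory, vital-sign and ECG tables belong to continuous summaries. A fixed FAS denominator with an explicit missing row would be defensible.

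Most of this stands and limits the weight of the point. It does not remove it: the missing total can be recovered by subtraction, but its reason cannot, and the physical-examination table shows that the SAP uses an assessed-only denominator for a categorical by-visit safety result.

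Three stronger readings are tempting, and the documents do not support them:

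- **That performance status will appear to worsen.** Dilution lowers grade 2 and above as well as grades 0 and 1, so the direction depends on who is missing.
- **That Visit 8 percentages fall in line with the discontinuation rate.** The early end-of-treatment assessment means that many who stop treatment should still contribute an ECOG. Those lost, withdrawn or dead may not.
- **That whole sites will skip five visits.** Protocol section 8.1.2 lists ECOG as a safety evaluation, and section 8 places safety assessments at the start of each cycle and requires adherence to the schedule of activities. Section 8.1.1 can be read as a minimum for response visits, although it uses mandatory wording and does not mention the per-cycle schedule. The documents give no share of sites that would read it otherwise.

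**Conclusion.** The point holds as a defect of table design. The planned percentages equal the distribution among assessed patients multiplied by the fraction assessed, and that fraction is not shown. The distortion is proportional to the missing fraction: 40/50/10% prints as 32/40/8% at 20% unassessed, and one MCL patient is worth 10 points. The baseline mix and the missing rates are assumptions; the cohort sizes and the denominator rule are the plan's own.

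The direction is indeterminate, the intermediate visits are the most exposed, and Visit 8 depends on an unstated mapping rule. Because the analysis is descriptive and the counts are printed, the consequence is a misleading table, not a wrong trial conclusion. The difference between protocol section 8.1.1 and Table 1 is secondary: the passages need to be reconciled, but the rest of the protocol largely points to one reading.

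**What to change.** In SAP Table 14.3.6 and section 6.3.1:

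1. Add an ECOG assessed Yes/No row, or n and Missing rows, at each visit, and base grade percentages on patients assessed at that visit.
2. Add a table of shifts from baseline to worst and to last on-treatment grade, by cohort. This is needed because an assessed-only denominator describes only those still attending.
3. State whether an early end-of-treatment assessment is tabulated at Visit 8 or at the visit where it occurred.
4. State whether a death is counted as grade 5 once, at all later visits, or as missing.

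Separately, reconcile the ECOG timing in protocol section 8.1.1 with Table 1, and have the SAP state the visits at which an assessment is expected.

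The SAP changes cost one footnote, one or two rows, a small shift table and two sentences, and need no new data. Changing the protocol wording is an amendment and, under Appendix A 1, needs ethics committee approval, so it could be combined with any other amendment.

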**Listing 16.2.1.1. Listing of Patient Informed Consent Details**

Patient Number	Patient Group	Informed consent	Date and Time for Informed Consent
xx-xxxx	(CLL/SLL)/(MCL)	Yes/No	DD-MMM-YYYY/HH:MM
xx-xxxx	(CLL/SLL)/(MCL)	Yes/No	DD-MMM-YYYY/HH:MM
xx-xxxx	(CLL/SLL)/(MCL)	Yes/No	DD-MMM-YYYY/HH:MM
xx-xxxx	(CLL/SLL)/(MCL)	Yes/No	DD-MMM-YYYY/HH:MM
xx-xxxx	(CLL/SLL)/(MCL)	Yes/No	DD-MMM-YYYY/HH:MM

Document Title:	Document ID:	BP04-01
Statistical Analysis Plan	Version Number:	3.1
	Effective Date:	25-Nov-2021

**Listing 16.2.1.2. Listing of Patient Study Completion**

Patient Number	Patient Group	Patient completed the study	Date of study completion/discontinuation	Primary reason for withdrawal	Other, specify
xx-xxxx	(CLL/SLL)/(MCL)	Yes/No	DD-MMM-YYYY	Xxxx	Xxxx
xx-xxxx	(CLL/SLL)/(MCL)	Yes/No	DD-MMM-YYYY	Xxxx	Xxxx
xx-xxxx	(CLL/SLL)/(MCL)	Yes/No	DD-MMM-YYYY	xxxx	xxxx
xx-xxxx	(CLL/SLL)/(MCL)	Yes/No	DD-MMM-YYYY	xxxx	xxxx
xx-xxxx	(CLL/SLL)/(MCL)	Yes/No	DD-MMM-YYYY	xxxx	xxxx

Document Title:	Document ID:	BP04-01
Statistical Analysis Plan	Version Number:	3.1
	Effective Date:	25-Nov-2021

